1.3.5.3. Pharmacokinetic and Pharmacodynamic Parameters

During the study, PK serum samples will be analyzed for concentrations of free MT-3724 and if indicated may also be analyzed for any other anti-CD20 biologic agent which the subject may have received prior to enrolment. Analysis of PK/PDn parameters will be described in a separate PK/PDn analysis document.

1.3.5.4. Immunogenicity

Immunogenicity parameters will be described in a separate analysis document.

2. SUBJECT POPULATION

2.1. Population Definitions

The following subject populations will be evaluated and used for presentation and analysis of the data:

- Safety Set (SS): All subjects who received any amount of MT-3724.
- Pharmacokinetic Analysis Set (PAS): All subjects from the Safety Set with sufficient serum concentration data to determine the primary PK parameters.
- Full Analysis Set (FAS): All subjects from the Safety Set who have at least one tumor re-evaluation performed (scheduled or unscheduled).

The Safety Set is the primary population for the analysis of safety. The PAS is the primary population for all PK and PDn analyses. The FAS is the primary population for all exploratory efficacy analyses.

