## 9.2 Populations for Analyses

For purposes of analysis, the following populations are defined:

Population	Description
Full analysis set (FAS) population	All subjects who received at least 1 dose of MT-3724 monotherapy treatment. This will be the primary population for the assessment of efficacy endpoints.
Modified full analysis set (mFAS) population	All subjects who have at least 1 post-baseline efficacy assessment; subjects without a post-baseline efficacy assessment will not be considered evaluable for the primary efficacy analysis. Subjects who discontinue due to disease progression or die, prior to disease assessment will be included.
PK analysis population	All subjects who received any amount of MT-3724 and for whom the on-treatment PK data are considered to be sufficient and interpretable.
Immunogenicity analysis population	All subjects who have received any amount of MT-3724 and have valid post-baseline immunogenicity assessment will be included in the analysis set for the immunogenicity analysis.
Pharmacodynamic analysis population	All subjects who have received any amount of MT-3724 and have at least 1 valid post-baseline pharmacodynamic assessment.
Safety analysis population	All subjects who received at least 1 dose of MT-3724 monotherapy treatment. For this study, this is equivalent to the FAS population.

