1.2.1. Main Study

1.2.1.1. Primary Objectives

In Part 1, subjects with NHL or CLL were enrolled, and the primary objectives were:

- To define the maximum tolerated dose (MTD) of a single course of MT-3724 given on Days 1, 3, 5, 8, 10 and 12 at which there are negligible side effects (adverse events) and/or at which maximum pharmacokinetic (PK)/pharmacodynamic (PDn) parameter changes are observed.
 - The MTD was determined to be 75 mcg/kg/dose. However, due to safety concerns, an adjusted MTD (50 mcg/kg/dose) is used for Part 2.
- To determine PK and PDn profiles of a single course of MT-3724 in escalating dose cohorts.

In Part 2, up to 40 additional subjects with relapsed/refractory diffuse large B-cell lymphoma (DLBCL) will be treated with the adjusted MTD (50 mcg/kg/dose) of MT-3724 in the MTD expansion cohort. The primary objectives will be to:

- Identify the frequency and nature of clinical and laboratory adverse events (AEs), both reported and observed, as a measure of safety and tolerability over repeated cycles of MT-3724 at the adjusted MTD.
- Define the PK and PD profiles of MT-3724 at the adjusted MTD in this sub-population.

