¹ Height and weight are collected at the Screen visit. Weight is collected again at final safety visit 14-28 days after last infusion. The MT-3724 dose is calculated using Screening visit weight.

² For the first two infusions in Cycle 1 (Doses 1 & 2), vital signs (temperature, blood pressure, pulse, and respiration rate) will be collected at pre-dose prior to initiation of dosing on each dosing day, at 20, 40 and 60 min (\pm 5 min), at 90 min (\pm 10 min), at 2 hours (\pm 15 min) and no less than hourly (\pm 15 min) until the infusion is completed. For all other infusions, vital signs should be collected prior to the initiation of the infusion and at the conclusion of the infusion (\pm 15 min). Beyond these times and at all other infusions, subjects should be monitored as clinically indicated. The frequency of interim monitoring during and following all infusions beyond the second infusion should be determined by the Investigator based on the subject's clinical condition. In addition, in all subjects, orthostatic vital signs will be performed as needed after all doses prior to the subject standing or ambulating for any reason during the observation period.

³ Calculate estimated creatinine clearance by Cockcroft Gault formula.

⁴ All female subjects of child bearing potential must have a urine pregnancy test performed prior to the first dose of each new cycle of MT-3724 beginning with the first cycle and continuing through the last cycle. Pregnancy test should be done within 72 hours prior to the first dose of each new cycle.

⁵ Lymphocyte subset samples must be processed and shipped to the Central Laboratory according to Site Reference Manual and Laboratory Manual instructions. The baseline flow cytometry sample should be drawn at the Screening Visit whenever possible. If not obtained at the Screening Visit, the baseline flow cytometry sample may be drawn on Dose Day 1 prior to initiation of dosing. The sample drawn on Cycle 1 Day 8 (Visit 5, Dose 4) during the first cycle of MT-3724 should be drawn PRIOR to the initiation of Dose 4 infusion. Additionally, **Part 1 only: FOR SUBJECTS WITH CLL, flow assessment for minimal residual disease (MRD) will be obtained at Baseline and the Final Safety Assessment** respectively.

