4.4. Pharmacokinetic Evaluation

Pharmacokinetic analyses will be conducted using the PAS.

Analysis of PK and PDn parameters will be described in a separate PK/PDn analysis document.

A by-subject listing with all sampling times will be presented.

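### The SAP ties its primary pharmacodynamic population to the sufficiency of PK data and defines no pharmacodynamic set, so subjects with valid PD results can fall outside the primary PD summary

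*SAP*

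**What the plan says.** SAP 2.1 lists a Safety Set, a PK set and a Full Analysis Set. There is no pharmacodynamic set. The PK set is defined by PK data alone: "Pharmacokinetic Analysis Set (PAS): All subjects from the Safety Set with sufficient serum concentration data to determine the primary PK parameters". The same section then names the population for pharmacodynamics: "The PAS is the primary population for all PK and PDn analyses".

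Pharmacodynamics is part of the primary objectives in SAP 1.2.1.1. For Part 1 the objective is "To determine PK and PDn profiles of a single course of MT-3724 in escalating dose cohorts". For Part 2 it is "Define the PK and PD profiles of MT-3724 at the adjusted MTD in this sub-population".

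The methods are deferred in SAP 4.4: "Analysis of PK and PDn parameters will be described in a separate PK/PDn analysis document". That document was not supplied.

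Protocol v11, section 9.2, which governs Parts 3 and 4, gives pharmacodynamics its own population: "All subjects who have received any amount of MT-3724 and have at least 1 valid post-baseline pharmacodynamic assessment".

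**The concern.** Describing the change in a blood marker by dose cohort needs a baseline value, a later value and the dose given. It does not need a serum concentration. The SAP nevertheless makes calculable PK parameters the condition for entering the primary PD analysis. A subject whose post-infusion draws were missed, mistimed or lost would leave the primary PD summary for a reason unrelated to the quality of the PD measurement.

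Two things are at stake. The first is precision, because Part 1 cohorts are planned at 3 to 6 subjects. The second is possible bias, if the reason for insufficient PK data is also related to PD response. In addition, the SAP defines neither what counts as sufficient nor which PK parameters are primary. Membership of the population for a primary objective is therefore left to judgement.

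**Working it through.** The plan states no figure to reproduce. The check compares definitions and schedules, followed by simple arithmetic.

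**1. Can a subject have valid PD data and fail the PAS condition?**

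| Item | Pharmacodynamics (flow cytometry) | Pharmacokinetics |
|---|---|---|
| Source | SAP 1.3.4, Tables 1 and 2, footnote 5 | SAP 1.3.4, Tables 1 and 2, footnote 8 |
| Cycle 1 timing | Screening (or Day 1 before dosing), Day 8 before infusion, Visit 9 (Days 23-25, Part 1 only), final safety visit | Day 1 at eight time points, Day 5, Day 8 before infusion, Day 12, Visit 9, final safety visit |
| Later cycles | Cycle 4 Day 1, final safety visit | First visit of each cycle, final safety visit |
| Handling | Own rule: "Lymphocyte subset samples must be processed and shipped to the Central Laboratory" | Timed serum samples, mainly around and after the end of infusion |

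The visits overlap, but the samples and assays differ. The parameters that decide PAS entry rest mainly on the timed post-infusion draws. A subject can lose those and still have a valid baseline and Day 8 flow result. The answer is yes.

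One assumption is needed: the SAP does not list its PDn parameters. Flow cytometry is taken as the natural example because the SAP schedules it, and because protocol v11, section 8.7.1, names B-cell count and immunophenotype as PD markers for Parts 3 and 4.

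**2. What happens to that subject under SAP 2.1?**

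The subject is in the Safety Set, is not in the PAS, and so is not in the primary population for PDn analyses. No other set is assigned to PD.

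**3. Cost in precision of one excluded subject**

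Inputs: Part 1 cohort size 3 to 6 (SAP 1.3.1.1); Part 2 maximum of 40 (SAP 3.1). Share lost = 1/n. With an unchanged standard deviation, the standard error of a mean grows by √(n/(n−1)).

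- n = 3: 1/3 = 33.3%; √(3/2) = 1.22
- n = 6: 1/6 = 16.7%; √(6/5) = 1.10
- n = 40: 1/40 = 2.5%; √(40/39) = 1.01

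**4. Possible bias (illustration only)**

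Let q be the share of PD-evaluable subjects outside the PAS, and d the mean PD change in retained subjects minus that in excluded subjects. The mean over everyone is (1−q)·(retained mean) + q·(excluded mean), so the PAS mean differs from it by q·d.

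The documents give neither q nor d. The assumed ranges are q from 5% to 20% and d from 0 to 60 percentage points in either direction.

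- Subjects affected: 0.05×20 = 1 to 0.20×20 = 4 of 20; 0.05×40 = 2 to 0.20×40 = 8 of 40
- d = 0: shift 0, so only precision is lost
- q = 0.10, d = 40: shift 4 points
- q = 0.20, d = 60: shift 12 points

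These figures show how the shift scales. They do not estimate what happened in the trial.

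**5. Would subjects with unmeasurable drug be excluded?**

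The supplied SAP has no rule for concentrations below quantification, although the term is in its abbreviation list. If such values were set to 0, as protocol v11, section 9.3.4.1, does for Parts 3 and 4, Cmax and AUC over 0 to 4 hours could be determined as 0, and the subject might stay in the PAS. Half-life and clearance could not be determined. The outcome turns on which parameters are primary, and the SAP does not say.

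**The case against.** The strongest case for leaving the text alone has four parts.

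- **Primary does not mean exclusive.** SAP 2.1 names the PAS as the primary population and forbids no supportive summary in another set. SAP 3.10 puts all case report form data in listings, SAP 4.6.2 lists all laboratory data, and 4.6.2 also summarises immunology and cytokine results within the safety section. This stands: the data are not discarded. It does not restore such subjects to the primary PD summary.
- **A separate PK/PDn document may settle it.** It may define sufficiency or the handling of low concentrations. However, SAP 4.4 assigns it the analysis of parameters, whereas SAP 1.2 says the SAP itself contains the population definitions, and 2.1 covers all PDn analyses. That document would have to depart from 2.1 to change the population.
- **The situation may be rare.** Day 1 alone has eight PK time points, all before the first post-baseline flow sample, and PK is also scheduled at the Cycle 1 visits where flow is drawn. This stands as a limit on size, since no rate of insufficient PK is given.
- **Protocol v11 is a different design.** This also stands. The SAP rests on protocol v7.0 and Parts 1 and 2, so section 9.2 of v11 is not a contradiction. It only shows a workable definition.

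A reader might also infer that subjects with unmeasurable drug are removed selectively, and that the PD effect at low doses is therefore overstated. The documents do not support that. No text says so, and the result depends on undefined terms and on a missing rule for low concentrations. PK data may equally be missing for sampling reasons unrelated to response.

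**Conclusion.** The point holds as a minor and easily removed defect. Read as written, SAP 2.1 makes PK sufficiency the gate to the primary analysis of a primary objective and offers no PD set. Subjects with valid PD results and insufficient PK data then fall outside the primary PD summary.

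The certain cost is precision. It is noticeable if it strikes a Part 1 cohort and slight in a full Part 2. Bias is possible but cannot be signed or sized from the documents. The conclusion assumes that at least one subject has valid PD and insufficient PK data, which the schedules permit but the documents do not report. No test result depends on it, because the SAP plans none (3.2).

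**What to change.** In SAP 2.1:

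- Add a pharmacodynamic set: all Safety Set subjects with a baseline and at least one valid post-baseline PD result. This follows the protocol v11 model, with an explicit baseline requirement because change from baseline needs one.
- Change the assignment sentence so that this set is the primary population for PD summaries. Keep the PAS for PK and for exposure-response analyses that need both kinds of data.
- State what counts as sufficient serum data, which PK parameters are primary, and how concentrations below quantification are handled. PAS membership then follows a rule and not judgement.

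The separate PK/PDn document should use the same sets. The core change is one definition and one sentence, with a small amount of programming and no new data collection. The third item adds a few lines of text.

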2.2. Protocol Violations

The Sponsor or designee will be responsible for producing the final protocol violation file (formatted as a Microsoft Excel file), in collaboration with Veristat and the data monitoring group as applicable; this file will include a description of the protocol violation. This file will be finalized prior to hard database lock.

All protocol violations will be presented in a data listing.

2.3. Withdrawals and Subject Replacement

Subjects may be withdrawn at any time for reasons including the following:

- at their own request or at the request of their legally authorized representative,
- if, in the Investigator's or Sponsor's opinion, continuation in the study would be detrimental to the subject's well-being, and/or
- when Stopping Rules have been met.

2.3.1. Main Study

Part 1: If a subject terminates study participation prior to per protocol Core Study completion the Investigator or their representative should notify Molecular Templates and the CRA immediately. In all cases, the reason for withdrawal must be recorded in the eCRF and in the subject's medical records. If the reason is not known, the subject must be followed to establish whether the reason was an AE, and, if so, this must be recorded. If a subject withdraws for reasons other than a DLT and prior to completing the Core Study Molecular Templates and the CRA must be informed immediately so a timely decision can be made regarding replacement of the subject. If a subject withdraws because of disease progression prior to completion of the Core Study, Molecular Templates and the CRA must be informed immediately so a timely decision can be made regarding replacement of the subject. Subjects in any cohort will not be replaced if they are withdrawn because of a DLT in the Core Study or they are withdrawn because of an AE or disease progression in the Repeat Dosing Study.

Part 2: If a subject terminates study participation prior to per-protocol post-Cycle 2 tumor assessment for any reason other than progressive disease, the Investigator or their representative should notify Molecular Templates and the CRA immediately. In all early withdrawal cases, the reason for withdrawal must be recorded in the CRF and in the subject's medical records. If the reason is not known, the subject must be followed up to establish whether the reason was an AE, and, if so, this must be recorded. If a subject terminates study participation prior to per-protocol post-Cycle 2 tumor assessment for any reason other than progressive disease, the Investigator or their representative should notify Molecular Templates and the CRA immediately. The DMC must review the study data from any subject who withdraws from the study prior to completing at least eight of twelve infusions in Cycles 1 and 2 and completing the post-Cycle 2 tumor reassessment. If withdrawal is for any reason other than disease progression, the DMC must review all safety data available for that subject and determine if the subject should be replaced in the MTD expansion cohort.

2.3.2. Extension Study

If a subject terminates study participation prior to per protocol completion of 6 cycles the Investigator or their representative should notify Molecular Templates and the CRA immediately. In all cases, the reason for withdrawal must be recorded in the case report form (CRF) and in the subject's medical records. If the reason is not known, the subject must be followed to establish whether the reason was an adverse event, and, if so, this must be recorded. The Investigator will make every effort to contact subjects lost to follow-up. Subjects withdrawing from this open access extension study due to an MT-3724 related toxicity will not be eligible for further MT-3724 treatment.

If a subject is discontinued early from the study for any reason after receiving one or more doses of MT-3724, they will be requested to undergo all the same safety assessments as outlined for the final assessment and exploratory efficacy examinations within 14 to 28 days of withdrawal that the subjects who complete the study are required to undergo.

3. GENERAL STATISTICAL METHODS

3.1. Sample Size Justification

Part 1: An estimated 20 to 40 subjects will be enrolled in this standard 3+3 cohort expansion safety and tolerability dose escalation study. The dose escalation cohorts will proceed per protocol as follows:

- Cohort 1: 5mcg/kg/dose/day
- Cohort 2: 10mcg/kg/dose/day
- Cohort 3: 20mcg/kg/dose/day
- Cohort 4: 50mcg/kg/dose/day
- Cohort 5: 100mcg/kg/dose/day
- Cohort 6: 75mcg/kg/dose/day

If the MTD is not reached at or prior to completion of Cohort 6 (75 mcg/kg/day) then additional cohorts will be added in incremental increases based upon analysis of PK/PD data and all safety data for previous cohorts. Additional dose exploration may be required to more accurately identify an MTD.

Part 2: A maximum of 40 DLBCL subjects will be treated in Part 2 (MTD Expansion). The cohort designation for Part 2 is Cohort 7 (50 mcg/kg/dose/day). Three patients started in Part 2 on 75 mcg/kg/day.

3.2. General Methods

All data listings that contain an evaluation date will contain a relative study day (Rel Day). Pre-treatment and on-treatment study days are numbered relative to the day of the first dose of study medication which is designated as Day 1. The preceding day is Day -1, the day before that is Day -2, etc.

All output will be incorporated into Rich Text Format (RTF) files, sorted and labeled according to the International Conference on Harmonisation (ICH) recommendations, and formatted to the appropriate page size(s).

Tabulations will be produced for appropriate demographic, baseline, efficacy, and safety parameters. For categorical variables, summary tabulations of the number and percentage of subjects within each category (with a category for missing data) of the parameter will be presented. For continuous variables, the number of subjects, mean, median, standard deviation (Std Dev), minimum, and maximum values will be presented. Time-to-event data will be summarized using Kaplan-Meier methodology using 25th, 50th (median), and 75th percentiles with associated 2-sided 95% confidence intervals (CIs), as well as percentage of censored observations.

This study is primarily descriptive in nature; therefore, there are no formal statistical hypothesis tests planned. Hypothesis testing may be employed if warranted.

3.3. Computing Environment

All descriptive statistical analyses will be performed using SAS statistical software v9.4, unless otherwise noted. Medical history and adverse events will be coded using the Medical Dictionary for Regulatory Activities (MedDRA) v17.0. Concomitant medications will be coded using the World Health Organization (WHO) Drug Dictionary version March 2014.

3.4. Baseline Definitions

For both the Main and Extension studies, unless noted otherwise, baseline will be defined as the most recent measurement prior to the first administration of MT-3724 in the Main Study.

3.5. Methods of Pooling Data

Subject data from all study centers will be combined for analysis.

3.6. Adjustments for Covariates

No formal statistical analyses that adjust for possible covariate effects are planned.

3.7. Multiple Comparisons/Multiplicity

Multiplicity is not of concern for this study with a descriptive interpretation.

3.8. Subpopulations

All safety and efficacy analyses will be conducted in the following subsets in addition to the overall population:

1. DLBCL vs. “mixed” or “transformed” DLBCL histology (where data allows), designated as NHL histological subtype.
2. Patients with negative vs. positive serum rituximab (RTX) level at screening in the overall population, designated as serum rituximab status at screening.
3. Patients with negative vs. positive serum RTX levels at screening in the DLBCL subsets as defined in point #1 (where data allows).

For Part 1, subjects who have a reported disease histology of Follicular Lymphoma at their initial screening diagnosis and who subsequently have a DLBCL histology at their diagnosis screening review visit will be considered as “Mixed” or “transformed” DLBCL. For Part 2, “mixed” or “transformed” histology is an allowed entry on the disease histology field on the eCRF, and is reported as such.

The distinction between negative and positive serum RTX level is as follows:

- For subjects tested using the RUO assay with a quantitative readout in ng/mL, RTX status will be based on the Sponsor-preferred clinical cut off defined as: <500 ng/mL = negative; >=500 ng/mL = positive.
- For subjects tested using the GLP assay with a semi-quantitative readout of ‘Negative’, ‘Low Positive’ or ‘High Positive’, RTX status will be defined as Positive if the readout is either ‘Low Positive’ or ‘High Positive’, and Negative if the readout is ‘Negative’.

Both types of results will be pooled for the analyses by serum RTX status.

3.9. Withdrawals, Dropouts, Loss to Follow-up

Subjects withdrawing from a cohort in Part 1/Core Study for reasons other than a DLT will be replaced. Subjects participating in Part 2 (MTD Expansion) who are withdrawn any time before Day 21 due to disease progression will be replaced. Subjects participating in Part 2 who withdraw prior to completion of the post-Cycle 4 tumor reassessment may be replaced at the Sponsor's discretion.

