1.3.5.2. Efficacy Parameters

As this is a dose finding study and is designed to assess the safety and tolerability of MT-3724, all efficacy analyses are exploratory in nature, based on documented tumor responses.

Tumor response following completion of even numbered (e.g., 2, 4, etc.) courses of MT-3724 and at final safety assessment following termination of MT-3724 will be assessed according to the Tumor Response Criteria for malignant lymphoma ([Cheson et al 2007](#)) defined by the International Working Group.

In addition, source document verified tumor lesion measurement data that was not reported in the EDC was collected and tallied by the Sponsor via an Excel Spreadsheet. The data in this Spreadsheet will be used for the analysis of percent change in tumor size.

Endpoints will include:

- Best Overall Response.
- Objective response rate (ORR) - Objective response will be determined as the proportion of subjects with either CR or PR using the tumor response criteria described below.
- Disease Control Rate (DCR) will be calculated as the proportion of subjects who achieve either CR, PR or stable disease status.
- Duration of tumor response (DOR) - Duration of response is defined as the time from the first occurrence of either complete or partial response to first documented evidence of disease recurrence or progression. Subjects without evidence of progression will be censored at time of last disease assessment. Only responders (CR or PR) will be included for this analysis.
- Progression-free survival (PFS) – Progression-free survival is calculated from the date of first infusion of MT-3724 to first documented evidence of disease recurrence or progression or death due to any cause. Subjects who are last known to be alive and without evidence of progression will be censored at time of last disease assessment.
- Duration of stable disease (i.e., duration of disease control) - Duration of at least stable disease is defined as the time from the date of first infusion of MT-3724 to first

documented radiologic evidence of disease recurrence or progression. Subjects without evidence of progression will be censored at time of last disease assessment.

- Overall survival (OS) – Overall survival is calculated from the date first dose of study treatment to the date of death. Subjects who are still alive prior to the data cutoff for final efficacy analysis, or who dropout prior to study end, will be censored at the day they were last known to be alive.

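### The SAP's efficacy set can omit Part 2 subjects who progress early and are never rescanned, which raises ORR and DCR; SAP 3.9 and 2.3.1 also give different replacement rules

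*SAP*

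**What the plan says.** **Analysis set.** SAP Section 2.1 defines the FAS as "All subjects from the Safety Set who have at least one tumor re-evaluation performed (scheduled or unscheduled". It adds: "The FAS is the primary population for all exploratory efficacy analyses".

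**Timing of scans.** SAP Section 1.3.5.2 assesses "Tumor response following completion of even numbered (e.g., 2, 4, etc.) courses of MT-3724 and at final safety assessment following termination of MT-3724". In the schedules of assessments (SAP Section 1.3.4, Tables 1 and 2), the radiology entry at the Final Safety Assessment is marked optional.

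**Response rate.** The same Section 1.3.5.2 states: "Objective response will be determined as the proportion of subjects with either CR or PR using the tumor response criteria described below". It defines DCR in the same way, with stable disease added. Section 3.10 makes no substitution for missing data points.

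**Replacement in Part 2.** Section 3.9 says that subjects "who are withdrawn any time before Day 21 due to disease progression will be replaced", and that subjects "who withdraw prior to completion of the post-Cycle 4 tumor reassessment may be replaced" at the sponsor's discretion. Section 2.3.1 gives a different route. It has the DMC review subjects who leave before completing enough infusions in Cycles 1 and 2 and the post-Cycle 2 scan. It then says: "If withdrawal is for any reason other than disease progression, the DMC must review all safety data available for that subject", and the DMC is to "determine if the subject should be replaced in the MTD expansion cohort".

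**The concern.** Membership of the efficacy set depends on something that happens after treatment starts, namely being rescanned. Subjects who deteriorate quickly are the least likely to reach a scan. If they leave the denominator, the response rate is calculated on a group from which some treatment failures have been removed, and the error can only go upward.

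The replacement rule makes this harder to see. A cohort that is topped up each time a subject progresses early looks complete, even though more subjects were treated than appear in the efficacy tables.

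Separately, two sections of one SAP tell the study team different things about who is replaced in Part 2 and who decides. That affects how many subjects are treated and which of them a reader takes to be the Part 2 cohort.

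**Working it through.** **There is no stated figure to reproduce.** SAP Section 3.1 caps Part 2 at 40 subjects and gives no target response rate, alpha or power. Section 3.2 plans no formal hypothesis test.

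**Step 1: can an early progressor lack a re-evaluation?** Part 2 cycles last at least 21 days (SAP Section 1.3.1.1), so the first routine response scan, after Cycle 2, falls no earlier than about 2 × 21 = 42 days. No routine scan falls before Day 21. The remaining chances are an unscheduled scan or the optional scan at the final visit. A subject withdrawn for clinical progression who has neither is in the Safety Set but not in the FAS.

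**Step 2: effect on the rates.** Let N be the number treated, R the number of responders, and m the number of early progressors with no scan of any kind.

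- ORR, all treated = R/N
- ORR, SAP FAS = R/(N − m)
- Inflation factor = N/(N − m)

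None of the m subjects can count as CR, PR or SD, so the same factor applies to DCR.

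The documents give neither R nor m. Assumed here: N = 40 (the cap), R = 6, 8 or 12, and m = 0 to 8.

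| m | Factor 40/(40 − m) | R = 6 | R = 8 | R = 12 |
|---|---|---|---|---|
| 0 | 1.00 | 15.0% | 20.0% | 30.0% |
| 2 | 1.05 | 15.8% | 21.1% | 31.6% |
| 4 | 1.11 | 16.7% | 22.2% | 33.3% |
| 8 | 1.25 | 18.8% | 25.0% | 37.5% |

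For R = 8, the exact 95% intervals are 9.1–35.6% (8/40), 10.1–39.2% (8/36) and 11.5–43.4% (8/32).

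**Step 3: what replacement adds.** Suppose the cohort is refilled until 40 subjects are in the FAS, with 8 responders. The SAP would report 8/40 = 20.0%. On all treated subjects, the rate is 8/44 = 18.2% if 4 unscanned subjects were replaced, and 8/48 = 16.7% if 8 were. If those replaced subjects had been scanned, they would stay in the FAS and it too would give 18.2% or 16.7%. The gap therefore comes from the FAS scan requirement. Replacement only restores the apparent cohort size.

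**Step 4: the two replacement rules side by side.**

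| | SAP 3.9 | SAP 2.3.1 |
|---|---|---|
| Reason | Progression before Day 21; also other early withdrawals | Reasons other than progression |
| Decision | Automatic for progression; otherwise the sponsor | DMC, case by case |
| Time point | Day 21, or post-Cycle 4 scan | 8 of 12 infusions and post-Cycle 2 scan |

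The rules differ on all three counts.

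**The case against.** **Early progressors need not leave the FAS.** Any re-evaluation counts, scheduled or not, and Section 1.3.5.2 names the final safety assessment as a time for response assessment. A subject whose progression was seen on a scan stays in as a non-responder. This stands. A reader might infer that the FAS drops every early progressor, and so divide the all-treated ORR by one minus the early-progression rate. An assumed 25% would then become 27.8%, 31.3% or 35.7% at early-progression rates of 10%, 20% or 30%. That holds only if none of those subjects was scanned, so it is an upper limit.

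**Replacement does not inflate the rate.** This also stands. The SAP nowhere removes replaced subjects from the Safety Set or the FAS, so deleting the Day 21 sentence alone would leave the bias untouched.

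**Section 2.3.1 does not forbid replacing Part 2 progressors.** This is correct. Its statement that certain subjects are not replaced is in the Part 1 paragraph. For progressors the conflict is by implication, because the Part 2 paragraph provides a replacement decision only for other reasons. The differences in decision-maker and time point are explicit.

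**The consequence is limited.** Part 2's primary objectives are safety and PK/PD, all efficacy is exploratory, and SAP Section 4.1 tabulates the number in each population with reasons for exclusion, so a careful reader could find the omitted subjects. That makes the loss detectable but does not correct the rate.

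**The text is incomplete.** Much of SAP Section 4.3 is missing from the public copy. A supportive all-treated analysis or a non-responder rule may stand there; none appears in the readable text.

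**Conclusion.** The concern holds as a conditional, upward bias. The SAP's FAS can omit treated Part 2 subjects who progress early and are never rescanned, and this multiplies ORR and DCR by N/(N − m). With 40 treated, the factor is 1.05 for m = 2 and 1.25 for m = 8. It is 1.00 if every such subject had any scan. N, R and m are assumptions, and the documents do not allow the actual size to be calculated. At R = 8 the largest shift shown is 5 percentage points, against an exact interval 35.6 − 9.1 = 26.5 points wide. The replacement rules in 3.9 and 2.3.1 differ regardless of any assumption and need reconciling.

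Two stronger inferences are not supported.

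- A reader might take the Part 2 response rate as the evidence for continuing in DLBCL. Protocol Section 4.1 refers to preliminary data at doses up to and including the MTD, and Section 2.2.1 to activity in the monotherapy study. Neither shows that Part 2 FAS figures are the source.
- A reader might carry the bias into Parts 3 and 4. Protocol v11.0 defines the FAS as all dosed subjects (Section 9.2), treats undeterminable responses as non-responses (Section 9.3.2.1) and limits replacement to undosed or DLT-unevaluable subjects (Section 7.2). This SAP is based on protocol v7.0.

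**What to change.** 1. Make all subjects who received MT-3724 (the Safety Set) the primary population for ORR and DCR. Count anyone without a tumor re-evaluation as a non-responder and as not having disease control. The present FAS can stay as a supportive analysis.
2. State that replaced subjects remain in every denominator, and report how many were replaced and why.
3. Give one Part 2 replacement rule, worded alike in Sections 3.9 and 2.3.1, covering reason, decision-maker and time point. Take it from the governing protocol (v7.0), which is not among the documents reviewed, so no choice between the two rules is made here.

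The cost is SAP wording, a rerun of the response tables and possibly a lower reported ORR and DCR. No new data are needed. The change would also put Part 2 on the same denominator and missing-response rules that protocol v11.0 uses for Part 4.
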